## **9.8. Subgroup Analyses**

No subgroup analyses are planned for this study.

## **9.9. Summary of Reasons for Efficacy Non-Evaluability /Exclusion from Efficacy Analyses**

The reasons for excluding subjects from the FAS and PP population will be listed by treatment and subject.

## 10. SAFETY AND TOLERABILITY

### 10.1. Overall Summary of Tolerability

The safety analyses will be based on the SAF, unless otherwise specified.

Table 12 provides an overview of the planned analyses.

**Table 12: Overview of Planned Safety Analyses**

Display Type	Data Displays Generated		
	Table	Figure	Listing
Adverse Events			
Overview	Y		
Treatment Emergent AEs	Y 		Y
Treatment-Related Emergent AEs	Y		Y
Pre-Treatment Period AEs	Y		Y
AEs Leading to Withdrawal			Y
SAEs	Y		Y
Treatment Emergent SAEs	Y		Y
Treatment-Related SAEs	Y		Y
Laboratory			
Biochemistry	Y 		Y
Hematology	Y 		Y
Urinalysis	Y 		Y
Pregnancy Test Results			Y
Other			
Vital Signs	Y 		Y
ECGs	Y 		Y
Physical Examination	Y 		Y

NOTES :

- Y = Yes display generated.
- [1]: Display will also be produced by severity, by relationship to study treatment and leading to discontinuation
- [2]: Display will be produced separately for overall laboratory assessments (inc. change from baseline), potentially clinically significant laboratory results, and shift tables
- [3]: Display will be produced separately for overall summary (inc. change from baseline), potentially clinically significant results, and shift tables
- [4]: Display will be produced separately for overall summary (inc. change from baseline), potentially clinically significant ECGs, and shift tables
- [5]: Display will be produced separately for overall summary

Safety will be assessed by evaluating AEs, SAEs, treatment related AEs and SAEs, vital signs, laboratory test results, ECG values, and physical examination findings. The extent of exposure in each treatment group will be characterized according to the number of subjects exposed, the duration of exposure, and the dose to which they were exposed. All safety analyses will be performed on the SAF.

## **10.2. Adverse Event Preferred Term and Body/Organ System Summary Tables**

### **10.2.1. Summaries of Adverse Event for All Subjects**

For each AE, the following information is to be recorded; the start date, the stop date (or whether the AE is ongoing at study completion/discontinuation), the severity and the investigator relationship of the AE to study drug, the therapy for the AE, the action taken with study drug, and whether or not the AE is considered serious.

Adverse events will be coded by system organ class (SOC) and preferred term (PT) using the Medical Dictionary for Regulatory Activities (MedDRA™) Version 18.0 or later.

Treatment Emergent AEs (TEAEs) are defined as AEs (identified by PT) that begins or that worsens in severity after at least one dose of study treatment has been administered, and last upto the AE stop date or the follow-up visit or the last study participation day. The number and percentage of subjects reporting at least one occurrence of a TEAE for each unique System Organ Class and Preferred Term will be tabulated by severity, and by the investigator relationship to study drug. For multiple occurrence of the same TEAE with the different severity, the TEAE with the highest severity will be tabulated. For multiple occurrences of the same TEAE with different relationship to study drug (related and not related), the TEAE will be tabulated as related. All TEAEs leading to discontinuation of treatment will also be tabulated. All AEs for all subjects will be presented in a data listing.

Pre-Treatment AEs (PTAEs) are defined as AEs (identified by PT) that begin or that worsen in severity between study Day -14 and study drug administration, and last up to the AE stop date.

The severity of AE is classified as follows:

Mild	The AE is a transient discomfort and does not interfere in a significant manner with the subject. The AE resolves spontaneously or may require minimal therapeutic intervention
Moderate	The AE produces limited impairment of function and may require therapeutic intervention. The AE produces no sequelae.
Severe	The AE results in a marked impairment of function and may lead to temporary inability to resume usual life pattern.
	The AE produces sequelae, which require (prolonged) therapeutic intervention.

The relationship of AEs to study medication is classified as follows:

- Not Related: A causal relationship between the study treatment and the AE is not a reasonable possibility

- Related: A causal relationship between the study treatment and the AE is a reasonable possibility

A COPD exacerbation is defined as worsening of the following 2 or more major symptoms for at least 2 consecutive days: dyspnea, sputum volume, and sputum purulence or a worsening of any 1 major symptom together with an increase in any 1 of the following minor symptoms for at least 2 consecutive days: sore throat, colds (nasal discharge and/or nasal congestion), fever without other cause, and cough. A COPD exacerbation shall be reported as an AE and may be considered serious if it meets the seriousness criteria for SAE reporting.

All serious AEs that occur after administration of the first dose of study drug will be listed by System Organ Class, Preferred Term, and relationship to study drug as assessed by the investigator. In addition to three treatment levels, a GSP 304 total will be presented in AE/SAE-related summary tables.

#### **10.2.2. Missing and Partial AE Onset Dates**

Refers to section 6.8.3

#### **10.2.3. Summaries of Serious Adverse Events (SAE), Adverse Event Dropouts, and Death**

For SAEs that are considered to be related to study drug, the number and percentage of subjects reporting at least one occurrence of an SAE for each unique System Organ Class will be tabulated. SAEs that lead to study discontinuation will be tabulated by unique System Organ Class, Preferred Term and relationship to study drug. All SAEs resulting in death will also be tabulated.

All SAEs will be presented for individual subjects in data listings, as well as premature discontinuations due to all causality. Deaths of all causes, study-drug related (occurring during study participation and up to 30 days post-treatment) or not, will be presented in a separate listing.

#### **10.3. Concomitant and Other Medications**

Concomitant medication will be coded by system organ class (SOC) and preferred term (PT) using the Medical Dictionary for Regulatory Activities (MedDRA™) Version 18.0 or later. Medical history data will be listed by treatment and subject

All concomitant medications taken since screening until the end of the study will be listed by treatment and subject.

#### **10.4. Laboratory Data**

Baseline and post-baseline clinical laboratory data (hematology, biochemistry, liver function, and urinalysis), will be summarized for Visit 4 to Visit 7 (the Final Visit). Descriptive statistics (number of subjects, mean, SD, median, minimum and maximum) will be presented for laboratory data as well as change from baseline by treatment and visit. In addition, values outside the respective normal range and values deemed as clinically significant by the Investigator will be listed.

The number of subjects with values of potential clinical significance determined by the investigator will be tabulated by treatment group and visit.

Shift tables will present changes from baseline in laboratory data (categorized as normal; abnormal, not clinically significant; and abnormal, clinically significant) to end of treatment.

All laboratory data will be listed by treatment and subject.

Estimated Glomerular filtration rate (eGFR) will be estimated using the Cockcroft-Gault approach.

#### **10.5. Vital Signs**

The subject's baseline and post-baseline vital signs will be recorded (pulse rates, sitting or lying down systolic and diastolic blood pressure) at Visits 3 to Visit 7. Height and weight will also be recorded at Screening Visit (Day -28 to Day -15). Descriptive statistics (number of subjects, mean, SD, median, minimum and maximum) will be used to summarize vital sign results and changes from baseline by treatment group and visit.

Values outside the respective normal range and values deemed as clinically significant by the Investigator will be listed.

The number of subjects with values of potential clinical significance determined by the investigator will be tabulated by treatment group and visit.

All vital sign data will be listed by treatment and subject.

#### **10.6. Electrocardiogram (ECG)**

Baseline and post-baseline electrocardiograms (12-lead ECG) will be performed at Visit 3 and Visit 6. The parameters to be reported are Heart Rate, PR Interval, QRS duration, QT interval, and QTc interval (QTcF and QTcB).

Descriptive statistics for ECG parameters and changes from baseline will be presented by treatment group. Shift tables will present changes from baseline to end of treatment in ECG interpretation (categorized as normal; abnormal, not clinically significant; and abnormal, clinically significant).

The number of subjects with values of potential clinical significance determined by the investigator will be tabulated by treatment group and visit.

All ECG data will be listed by treatment and subject.

## **10.7. Physical Examination**

Baseline and post-baseline physical examinations will be performed at Visit 3 to Visit 6.

Descriptive statistics (frequency and percentage) will be used to summarize physical examination results by body system, treatment group and visit. In addition, the number of subjects with values of potential clinical significance determined by the investigator will be tabulated.

All physical examination data will be listed by treatment and subject.

## **10.8. Study Termination Status**

If the Investigator or the Sponsor's Medical Monitor becomes aware of conditions or events that suggest a possible hazard to subjects if the study continues, the study may be terminated after appropriate consultation between the relevant parties. The study may also be terminated early at the Sponsor's discretion in the absence of such a finding.

Conditions that may warrant termination include, but are not limited to:

- The discovery of an unexpected, significant, or unacceptable risk to the subjects enrolled in the study;
- Failure to enroll subjects at an acceptable rate;
- A decision on the part of the Sponsor to suspend or discontinue development of the drug product.

## **10.9. Changes from Protocol**

The following changes from the protocol were made in the SAP.

1) The definition of the primary endpoint was clarified from change from baseline in trough forced expiratory volume in one second (FEV1) at 24 hours after the last dose of treatment on Day 21 in comparison with placebo to change from baseline (Day 1) at Day 21 (Week 3) in trough FEV1 response at approximately 24 hours after the last dose (average of 23 hours 15 minutes and 23 hours 45 minutes post-dose measurements).

2) The language used for definition of the secondary endpoint of change from baseline in trough FVC, and the associated analyses related to this endpoint, was modified to align it with the language that has been used for the primary endpoint.

3) The following secondary endpoints were added;

- Time to onset of response, defined as at least 12% and 200 mL increase in FEV1 within 12 hours of dosing on Day 1
- Time to achieving steady state as measured by FEV1 trough assessments
- Time to achieving steady state as measured by FVC trough assessments

4) Spirometry Effort Start Time: will use the first effort (Test 1) regardless of whether this is an acceptable effort or not. Instead of “start time of first spirometry effort” (per protocol), we are using the end time of the first spirometry effort.

## 12.2. Data Display Specification

Page XX of YY

Table 14.1.1  
Summary of Disposition

## All Screened Subjects

Glenmark Specialty SA  
 Statistical Analysis Plan - Protocol #GSP304-201

SEPT 12, 2017

Protocol Deviation	xx (xx.x)					
Violation of Inclusion/Exclusion Criteria	xx (xx.x)					
Withdrawal Criteria	xx (xx.x)					
Informed Consent	xx (xx.x)					
Treatment Administration	xx (xx.x)					
Prohibited Medications	xx (xx.x)					
Randomization Code Broken	xx (xx.x)					
Visit Schedule	xx (xx.x)					
Procedure/Tests	xx (xx.x)					
AE/SAE	xx (xx.x)					
Subject suffers from significant inter-current illness or undergoes surgery	xx (xx.x)					
Subject requires concomitant medication, which may interfere with the PK of study medication	xx (xx.x)					
Unable to comply with the spirometry washout criteria	xx (xx.x)					
COPD Exacerbation	xx (xx.x)					
Lost To Follow-up	xx (xx.x)					
Death	xx (xx.x)					
Pregnancy	xx (xx.x)					
Sponsor Decision	xx (xx.x)					
Non-Compliance with Study						
Drug	xx (xx.x)					
Other	xx (xx.x)					

[1] N1 is the number of screened subjects. Percentages are based on the number of screened subjects; [2] N2 is the number of randomized subjects. Percentages for all categories are based on the number of randomized subjects. n = Number of subjects with data in the summarized category

Program location/program name.sas/ddmmmyyyy/hh:mm

Source Data: Listing xxxxxxx Database Extract Date: ddmmmyyyy

Programming notes:

Table 14.1.2  
Summary of Subjects in Analysis Population

## Randomized Subjects

Percentages are based on the total number of randomized subjects in each treatment group. N = Number of randomized subjects; n = Number of subjects with data in the summarized category; Full analysis population includes all subjects who are randomized, have received at least 1 dose of study medication and have at least 1 post-baseline PD assessment; Safety population includes all subjects who are randomized and received at least 1 dose of study medication; Per-protocol population includes all subjects who are randomized, received at least 1 dose of study medication, completed the study and do not have exclusionary major protocol deviations; Pharmacokinetic population includes all subjects who are randomized, received at least 1 dose of study treatment and have at least 1 quantifiable PK sample and do not have exclusionary major protocol deviations.

Program location/program name.sas/ddmmmyyyy/hh:mm

Source Data: Listing xxxxxxx Database Extract Date: ddmmmyyyy

## Programming notes:

Table 14.1.3  
 Summary of Protocol Deviations

Safety Set

	GSP304				Spiriva R	
	(N=xxx) n (%)	(N=xxx) n (%)	(N=xxx) n (%)	Placebo (N=xxx) n (%)	5 ug (N=xxx) n (%)	Total (N=xxx) n (%)
Subjects with at least one PD	xx (xx.x)	xx (xx.x)	xx (xx.x)	xx (xx.x)	xx (xx.x)	xx (xx.x)
Subjects with at least one Major PD [1]	xx (xx.x)	xx (xx.x)	xx (xx.x)	xx (xx.x)	xx (xx.x)	xx (xx.x)
Category						
Violation of inclusion/exclusion Criteria	xx (xx.x)	xx (xx.x)	xx (xx.x)	xx (xx.x)	xx (xx.x)	xx (xx.x)
Withdrawal Criteria	xx (xx.x)	xx (xx.x)	xx (xx.x)	xx (xx.x)	xx (xx.x)	xx (xx.x)
Informed Consent	xx (xx.x)	xx (xx.x)	xx (xx.x)	xx (xx.x)	xx (xx.x)	xx (xx.x)
Treatment Administration	xx (xx.x)	xx (xx.x)	xx (xx.x)	xx (xx.x)	xx (xx.x)	xx (xx.x)
Prohibited Medications	xx (xx.x)	xx (xx.x)	xx (xx.x)	xx (xx.x)	xx (xx.x)	xx (xx.x)
Randomization Code Broken	xx (xx.x)	xx (xx.x)	xx (xx.x)	xx (xx.x)	xx (xx.x)	xx (xx.x)
Visit Schedule	xx (xx.x)	xx (xx.x)	xx (xx.x)	xx (xx.x)	xx (xx.x)	xx (xx.x)
Procedure/Tests	xx (xx.x)	xx (xx.x)	xx (xx.x)	xx (xx.x)	xx (xx.x)	xx (xx.x)
AE/SAE	xx (xx.x)	xx (xx.x)	xx (xx.x)	xx (xx.x)	xx (xx.x)	xx (xx.x)
Subjects with at least one Major PD leading to exclusion from PP						
Category						
Violation of inclusion/exclusion Criteria	xx (xx.x)	xx (xx.x)	xx (xx.x)	xx (xx.x)	xx (xx.x)	xx (xx.x)
Withdrawal Criteria	xx (xx.x)	xx (xx.x)	xx (xx.x)	xx (xx.x)	xx (xx.x)	xx (xx.x)
Informed Consent	xx (xx.x)	xx (xx.x)	xx (xx.x)	xx (xx.x)	xx (xx.x)	xx (xx.x)
Treatment Administration	xx (xx.x)	xx (xx.x)	xx (xx.x)	xx (xx.x)	xx (xx.x)	xx (xx.x)
Prohibited Medications	xx (xx.x)	xx (xx.x)	xx (xx.x)	xx (xx.x)	xx (xx.x)	xx (xx.x)
Randomization Code Broken	xx (xx.x)	xx (xx.x)	xx (xx.x)	xx (xx.x)	xx (xx.x)	xx (xx.x)
Visit Schedule	xx (xx.x)	xx (xx.x)	xx (xx.x)	xx (xx.x)	xx (xx.x)	xx (xx.x)
Procedure/Tests	xx (xx.x)	xx (xx.x)	xx (xx.x)	xx (xx.x)	xx (xx.x)	xx (xx.x)
AE/SAE	xx (xx.x)	xx (xx.x)	xx (xx.x)	xx (xx.x)	xx (xx.x)	xx (xx.x)

[1] Deviations which require exclusion from per-protocol and/or PKAS population. The final MPD categories and decision on deviations to be decided during the blinded data review process. Subjects may have more than one significant protocol deviation; N = Number of safety subjects; n = Number of subjects with data in the summarized category.

Program location/program name.sas/ddmmmyyyy/hh:mm  
Source Data: Listing xxxxxxx Database Extract Date: ddmmmyyyy

---

Programming notes:

Repeat for

Table 14.1.4 Summary of Protocol Deviations  
PK Analysis Set

---

Table 14.1.8.1  
 Summary of Demographic Characteristics

Full Analysis Set

Category/Statistics	GSP304				Spiriva R	
	(N=xxx) n (%)	(N=xxx) n (%)	(N=xxx) n (%)	Placebo (N=xxx) n (%)	5 ug (N=xxx) n (%)	Total (N=xxx) n (%)
Age (years)	n	xxx	xxx	xxx	xxx	xxx
	Mean (SD)	xx.x (x.xx)	xx.x (x.xx)	xx.x (x.xx)	xx.x (x.xx)	xx.x (x.xx)
	Median	xx.x	xx.x	xx.x	xx.x	xx.x
	Min; Max	xx; xx	xx; xx	xx; xx	xx; xx	xx; xx
Age Category (years)	≥ 40, <65	xx (xx.x)	xx (xx.x)	xx (xx.x)	xx (xx.x)	xx (xx.x)
	≥ 65, <85	xx (xx.x)	xx (xx.x)	xx (xx.x)	xx (xx.x)	xx (xx.x)
Sex	Female	xx (xx.x)	xx (xx.x)	xx (xx.x)	xx (xx.x)	xx (xx.x)
	Male	xx (xx.x)	xx (xx.x)	xx (xx.x)	xx (xx.x)	xx (xx.x)
Race	n	xxx	xxx	xxx	xxx	xxx
	Asian	xx (xx.x)	xx (xx.x)	xx (xx.x)	xx (xx.x)	xx (xx.x)
	Black/					
	African American	xx (xx.x)	xx (xx.x)	xx (xx.x)	xx (xx.x)	xx (xx.x)
	White	xx (xx.x)	xx (xx.x)	xx (xx.x)	xx (xx.x)	xx (xx.x)
	American Indian/					
	Alaska Native	xx (xx.x)	xx (xx.x)	xx (xx.x)	xx (xx.x)	xx (xx.x)
	Native Hawaiian/					
	other Pacific Islander	xx (xx.x)	xx (xx.x)	xx (xx.x)	xx (xx.x)	xx (xx.x)
	Multiple	xx (xx.x)	xx (xx.x)	xx (xx.x)	xx (xx.x)	xx (xx.x)
	Not Stated	xx (xx.x)	xx (xx.x)	xx (xx.x)	xx (xx.x)	xx (xx.x)
Ethnicity	Hispanic or Latino	xx (xx.x)	xx (xx.x)	xx (xx.x)	xx (xx.x)	xx (xx.x)
	Not Hispanic or Latino	xx (xx.x)	xx (xx.x)	xx (xx.x)	xx (xx.x)	xx (xx.x)
	Not Stated	xx (xx.x)	xx (xx.x)	xx (xx.x)	xx (xx.x)	xx (xx.x)

N = Number of full analysis subjects; n = Number of subjects with data in the summarized category

Program location/program name.sas/ddmmmyyyy/hh:mm

Source Data: Listing xxxxxxx Database Extract Date: ddmmmyyyy

---

Programming notes:

Repeat for

Table 14.1.8.2 Summary of Demographic Characteristics

Safety Set

Footnote: N = Number of safety subjects ; n = Number of subjects with data in the summarized category

Table 14.1.8.3 Summary of Demographic Characteristics

Per-Protocol Set

Footnote: N = Number of per-protocol subjects ; n = Number of subjects with data in the summarized category

Table 14.1.8.4 Summary of Demographic Characteristics

PK Analysis Set

Footnote: N = Number of PK analysis subjects ; n = Number of subjects with data in the summarized category

---

Table 14.1.9  
 Summary of Baseline Characteristics

Full Analysis Set

Category/Statistics	GSP304				Spiriva R	
	████████	████████	████████	Placebo	5 ug	Total
	(N=xxx) n (%)					
Height (cm)	n	xxx	xxx	xxx	xxx	xxx
	Mean (SD)	xx.x (x.xx)				
	Median	xx.x	xx.x	xx.x	xx.x	xx.x
	Min; Max	xx; xx				
Weight (kg)	n	xxx	xxx	xxx	xxx	xxx
	Mean (SD)	xx.x (x.xx)				
	Median	xx.x	xx.x	xx.x	xx.x	xx.x
	Min; Max	xx;xx	xx; xx	xx;xx	xx; xx	xx; xx
BMI (kg/m  )	n	xxx	xxx	xxx	xxx	xxx
	Mean (SD)	xx.x (x.xx)				
	Median	xx.x	xx.x	xx.x	xx.x	xx.x
	Min; Max	xx; xx	xx;xx	xx; xx	xx; xx	xx; xx
Smoking Status	Yes	xx (xx.x)				
	No	xx (xx.x)				
Number of Cigarette Pack (years)	n	xxx	xxx	xxx	xxx	xxx
	Mean (SD)	xx.x (x.xx)				
	Median	xx.x	xx.x	xx.x	xx.x	xx.x
	Min; Max	xx; xx				
Time from COPD Diagnosis (years)	n	xxx	xxx	xxx	xxx	xxx
	Mean (SD)	xx.x (x.xx)				
	Median	xx.x	xx.x	xx.x	xx.x	xx.x
	Min; Max	xx; xx				
Any COPD exacerbation in previous 3 months before screening [1]	Yes	xx (xx.x)				
	No	xx (xx.x)				

Number of COPD if [1] =Yes	n	xxx	xxx	xxx	xxx	xxx	xxx
	Mean (SD)	xx.x (x.xx)					
	Median	xx.x	xx.x	xx.x	xx.x	xx.x	xx.x
	Min; Max	xx; xx					
If [1] =Yes, was there any hospitalization?	Yes	xx (xx.x)					
	No	xx (xx.x)					

N = Number of full analysis subjects; n = Number of subjects with data in the summarized category

Program location/program name.sas/ddmmmyyyy/hh:mm

Source Data: Listing xxxxxxx Database Extract Date: ddmmmyyyy

---

Programming notes:

---

Table 14.1.10  
 Summary of Medical History per SOC and PT

Safety Set

System Organ Class Preferred Term	GSP304				Spiriva R	
	(N=xxx) n (%) [#]	(N=xxx) n (%) [#]	(N=xxx) n (%) [#]	Placebo (N=xxx) n (%) [#]	5 ug (N=xxx) n (%) [#]	Total (N=xxx) n (%) [#]
Any medical history	xx (xx.x) [#]	xx (xx.x) [#]	xx (xx.x) [#]	xx (xx.x) [#]	xx (xx.x) [#]	xx (xx.x) [#]
SOC #1	xx (xx.x) [#]	xx (xx.x) [#]	xx (xx.x) [#]	xx (xx.x) [#]	xx (xx.x) [#]	xx (xx.x) [#]
PT #1	xx (xx.x) [#]	xx (xx.x) [#]	xx (xx.x) [#]	xx (xx.x) [#]	xx (xx.x) [#]	xx (xx.x) [#]
...	xx (xx.x) [#]	xx (xx.x) [#]	xx (xx.x) [#]	xx (xx.x) [#]	xx (xx.x) [#]	xx (xx.x) [#]
SOC #2	xx (xx.x) [#]	xx (xx.x) [#]	xx (xx.x) [#]	xx (xx.x) [#]	xx (xx.x) [#]	xx (xx.x) [#]
PT #2	xx (xx.x) [#]	xx (xx.x) [#]	xx (xx.x) [#]	xx (xx.x) [#]	xx (xx.x) [#]	xx (xx.x) [#]
...	xx (xx.x) [#]	xx (xx.x) [#]	xx (xx.x) [#]	xx (xx.x) [#]	xx (xx.x) [#]	xx (xx.x) [#]
...						

SOC = System Organ Class; PT = Preferred Term; N = Number of safety subjects; n = Number of subjects reporting at least one medical history in that category; [#] = Number of individual occurrences of the medical history in that category

Program location/program name.sas/ddmmmyyyy/hh:mm

Source Data: Listing xxxxxxx Database Extract Date: ddmmmyyyy

Programming notes:

Ordered in terms of decreasing frequency for SOC, and PT within SOC, in the treatment group, and then alphabetically for SOC, and PT within SOC.

Table 14.1.11  
 Summary of Treatment Compliance

Safety Set

Category	Statistics	GSP304				Spiriva R	
		(N=xxx) n (%)	(N=xxx) n (%)	(N=xxx) n (%)	Placebo (N=xxx) n (%)	5 ug (N=xxx) n (%)	Total (N=xxx) n (%)
Number of Subjects Exposed		xx (xx.x)	xx (xx.x)	xx (xx.x)	xx (xx.x)	xx (xx.x)	xx (xx.x)
Average Daily Dose (ug) [1]	n	xxx	xxx	xxx	xxx	xxx	xxx
	Mean (SD)	xx.x (x.xx)	xx.x (x.xx)	xx.x (x.xx)	xx.x (x.xx)	xx.x (x.xx)	xx.x (x.xx)
	Median	xx.x	xx.x	xx.x	xx.x	xx.x	xx.x
	Min; Max	xx; xx	xx; xx	xx; xx	xx; xx	xx; xx	xx; xx
Nebulization Time (minute)	n	xxx	xxx	xxx	xxx	xxx	xxx
	Mean (SD)	xx.x (x.xx)	xx.x (x.xx)	xx.x (x.xx)	xx.x (x.xx)	xx.x (x.xx)	xx.x (x.xx)
	Median	xx.x	xx.x	xx.x	xx.x	xx.x	xx.x
	Min; Max	xx; xx	xx; xx	xx; xx	xx; xx	xx; xx	xx; xx
Number of Days on Treatment [2]	n	xxx	xxx	xxx	xxx	xxx	xxx
	Mean (SD)	xx.x (x.xx)	xx.x (x.xx)	xx.x (x.xx)	xx.x (x.xx)	xx.x (x.xx)	xx.x (x.xx)
	Median	xx.x	xx.x	xx.x	xx.x	xx.x	xx.x
	Min; Max	xx; xx	xx; xx	xx; xx	xx; xx	xx; xx	xx; xx
Number of Days on Study [3]	n	xxx	xxx	xxx	xxx	xxx	xxx
	Mean (SD)	xx.x (x.xx)	xx.x (x.xx)	xx.x (x.xx)	xx.x (x.xx)	xx.x (x.xx)	xx.x (x.xx)
	Median	xx.x	xx.x	xx.x	xx.x	xx.x	xx.x
	Min; Max	xx; xx	xx; xx	xx; xx	xx; xx	xx; xx	xx; xx
Compliance Group (%)	<80%	xx (xx.x)	xx (xx.x)	xx (xx.x)	xx (xx.x)	xx (xx.x)	xx (xx.x)
	≥80% - ≤100%	xx (xx.x)	xx (xx.x)	xx (xx.x)	xx (xx.x)	xx (xx.x)	xx (xx.x)
	>100% - <120%	xx (xx.x)	xx (xx.x)	xx (xx.x)	xx (xx.x)	xx (xx.x)	xx (xx.x)
	≥120%	xx (xx.x)	xx (xx.x)	xx (xx.x)	xx (xx.x)	xx (xx.x)	xx (xx.x)
Compliance (%)	n	xxx	xxx	xxx	xxx	xxx	xxx
	Mean (SD)	xx.x (x.xx)	xx.x (x.xx)	xx.x (x.xx)	xx.x (x.xx)	xx.x (x.xx)	xx.x (x.xx)
	Median	xx.x	xx.x	xx.x	xx.x	xx.x	xx.x
	Min; Max	xx; xx	xx; xx	xx; xx	xx; xx	xx; xx	xx; xx

[1] Average dose = Add up all dose taken by the subject and divided by the number of days in the study ;[2] Total number of dosing days from first to last day of dose; [3] Total number of days from study screening through to end of study/follow-up.

N = Number of safety subjects ; n = Number of subjects with data in the summarized category

Program location/program name.sas/ddmmmyyyy/hh:mm

Source Data: Listing xxxxxxx Database Extract Date: ddmmmyyyy

---

Programming notes:

SAP section 7.9

---

Table 14.1.12  
 Summary of Prior Medication

Safety Set

WHODD September v2015 WHO ATC Class	Anatomical Main Group [level 1]	GSP304			Placebo	Spiriva R 5 ug	Total
		(N=xxx) n (%)	(N=xxx) n (%)	(N=xxx) n (%)			
Any medical history		xx (xx.x)	xx (xx.x)	xx (xx.x)	xx (xx.x)	xx (xx.x)	xx (xx.x)
3-OXOANDROSTEN (4) DERIVATIVES, G03BA		xx (xx.x)	xx (xx.x)	xx (xx.x)	xx (xx.x)	xx (xx.x)	xx (xx.x)
GENITO URINARY SYSTEM AND SEX HORMONES, G		xx (xx.x)	xx (xx.x)	xx (xx.x)	xx (xx.x)	xx (xx.x)	xx (xx.x)
ANDROGENS, G03B		xx (xx.x)	xx (xx.x)	xx (xx.x)	xx (xx.x)	xx (xx.x)	xx (xx.x)
TESTOSTERONE		xx (xx.x)	xx (xx.x)	xx (xx.x)	xx (xx.x)	xx (xx.x)	xx (xx.x)
...							

N = Number of safety subjects; n = Number of subjects reporting at least one prior medication in that category

Program location/program name.sas/ddmmmyyyy/hh:mm

Source Data: Listing xxxxxxx Database Extract Date: ddmmmyyyy

Programming notes:

Repeat for

Table 14.1.13 Summary of Concomitant Medications

Footnote:

N = Number of safety subjects; n = Number of subjects reporting at least one concomitant medication in that category; [#] = Number of individual occurrences of the concomitant medication in that category

Table 14.1.14  
Summary of Rescue Medication Use (Reported in eDiary)

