**Reference therapy, dose and mode of administration:**

Name of Comparator: Spiriva® Respimat® inhalation spray 2.5 µg per actuation

Dosage Form: Inhalation Spray

Dosage: 5 µg (2 actuations of 2.5 µg each)

Dosage Frequency: Once Daily (QD)

Mode of Administration: By oral inhalation using Respimat® Soft Mist Inhaler

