**Duration of treatment:**

3 weeks (21 days)

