### **7.9. Total Duration of Therapy, Average Daily Dose, Maximum Daily Dose, Final Daily Dose of Study Medication, and Compliance**

The number of subjects exposed to each study treatment will be summarized.

The number of days on treatment and the number of days on study (screening through to end of study/follow-up) will be summarized by study treatment.

Treatment compliance will be calculated (the total number of doses actually taken / total number of doses expected\*100). For subjects who have completed the study:

Study Period	Duration	Scheduled Doses	Compliance Criteria	
			Not less than 80% (doses)	Not more than 120% (doses)
Randomized Treatment	21 Days	21	17	25

For subjects who are early terminated, treatment compliance will be determined from their duration in the study, up to the time they are considered early terminated. Subjects taking fewer than 80% or more than 120% of the required doses will be considered non-compliant with dosing.

In addition, treatment compliance will be classified into four categories (<80%,  $\geq 80\% - \leq 100\%$ ,  $>100\% - <120\%$ ,  $\geq 120\%$ ). Treatment compliance will be summarized by category and study treatment.

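### Table 14.1.11 divides total dose by days in the study, so average daily dose in the active arms would be reported at roughly one third of the dose actually given per treatment day

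*SAP*

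**What the plan says.** The SAP's Table 14.1.11 (section 12.2, summary of treatment compliance, Safety Set) has a row for average daily dose in µg. Its footnote [1] reads: "Average dose = Add up all dose taken by the subject and divided by the number of days in the study".

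The same table has two separate rows for time. Footnote [2] defines days on treatment as "Total number of dosing days from first to last day of dose". Footnote [3] defines days on study as "Total number of days from study screening through to end of study/follow-up". The text of section 7.9 makes the same distinction: it lists days on treatment and, separately, "the number of days on study (screening through to end of study/follow-up".

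Average daily dose appears in the heading of section 7.9, but the section gives no formula for it. The table's programming note only points back to that section, so footnote [1] is the sole definition a programmer has.

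Section 10.1 commits to describing exposure in each group by the number of subjects exposed, "the duration of exposure, and the dose to which they were exposed".

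**The concern.** An average daily dose should describe what a subject received per day of treatment. Footnote [1] instead takes its denominator from the whole study, including screening, run-in and follow-up, when no study drug is given. Two consequences follow.

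- Every active arm would be reported well below its assigned dose. A column headed Spiriva R 5 µg could show a mean near 1.7 µg/day in the same table as compliance near 100%. A reader would take that for under-dosing or a programming error.
- The value would depend on how long a subject spent in screening and when the follow-up visit fell. Neither has anything to do with exposure.

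In a dose-ranging study, the row that reports the dose received should at least agree with the doses compared.

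**Working it through.** The SAP states no value for average daily dose, so there is no published figure to reproduce. The check applies its formula to its own inputs, using the Spiriva arm because that dose is not redacted.

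**Inputs (all from the SAP)**
- Spiriva dose: 5 µg once daily (technical summary, reference therapy).
- Treatment: 21 days (technical summary), with 21 scheduled doses (section 7.9 table).
- Study periods: up to 2 weeks of screening, 2 of run-in, 3 of treatment and 2 of follow-up (section 4.1).
- Visit windows: screening Day -28 to -15; follow-up Day 33 to 37, scheduled Day 35 (Table 5).
- No study day 0 (section 6.7.2).

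**Length of study.** 2 + 2 + 3 + 2 = 9 weeks = 63 days, which matches the stated total of about 9 weeks. Counting days gives the same: Day -28 to Day 35 with no Day 0 is 28 + 35 = 63. The longest span in the windows is 28 + 37 = 65 days and the shortest is 15 + 33 = 48 days.

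**Total dose, full compliance.** 21 × 5 = 105 µg.

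**Average daily dose = 105 / denominator**

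| Denominator | Days | µg/day | Below 5 µg by |
|---|---|---|---|
| Screening to follow-up, nominal | 63 | 1.67 | 67% |
| Same, longest window | 65 | 1.62 | 68% |
| Same, shortest window | 48 | 2.19 | 56% |
| Randomization to Day 35 | 35 | 3.00 | 40% |
| Treatment days | 21 | 5.00 | 0% |

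Two equally dosed, fully compliant completers could differ by a factor of 65/48 = 1.35 through visit timing alone.

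**Other arms.** For any total dose T, the ratio of the two formulas is (T/63)/(T/21) = 21/63 = 1/3. The redacted GSP304 doses do not enter it. For placebo, with a unit dose of 0 µg (Table 3), both formulas give 0.

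**Which treatment-day denominator.** Footnote [2] can be read as a count of days on which a dose was taken or as the calendar span from first to last dose. These differ when doses are missed in between. Take a Spiriva subject who takes 17 of 21 doses, including those on Days 1 and 21: the total is 17 × 5 = 85 µg. Over the 21-day span this is 85/21 = 4.05 µg/day. Divided by the 17 days dosed it is 85/17 = 5.0 µg/day, so the missed doses disappear. Only the calendar span makes the row informative.

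**The case against.** The strongest reply is that the footnote is loosely worded rather than wrong. It does not use the row label for days on study and does not cite footnote [3]. Section 7.9, to which the programming note points, bases compliance of early terminators on their duration in the study. In that context this can sensibly mean only the dosing period, since no doses are expected before Day 1. The authors may well have meant treatment days here too.

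That stands as a statement about intent. It does not repair the text, which sits beside separate definitions of treatment days and study days and is worded like the latter. The narrower reading from randomization to Day 35 still gives 3.0, not 5.0.

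The reply is also right that the consequence is small. Days on treatment, compliance percentage and compliance category appear in the same table, so exposure can be recovered from them. Section 6.2 allows footnotes to be modified, and section 6.3 has outputs independently checked, so an implausible value might be caught. Neither provision corrects the derivation rule.

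A reader might infer that the error carries into Listing 16.2.5.3, which also shows average daily dose. The document does not say so: that shell has no formula, does not refer to footnote [1], and has a visit column that fits poorly with one whole-study average per subject.

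**Conclusion.** The concern holds as a wrong denominator in the only stated definition of a descriptive quantity. Following footnote [1], with study time taken from footnote [3] and section 7.9, understates average daily dose by 67% at the nominal 9 weeks and by 56% to 68% across the visit windows. This assumes a completer who takes all 21 doses. The proportional error is the same in every active arm for a given length of study; the placebo arm is unaffected.

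The reach is limited. A reader might infer that compliance, the per-protocol set or the primary results are compromised, but the documents do not support that. Compliance is doses taken over doses expected (section 7.9), and the per-protocol criterion in section 7.4 uses that percentage. The PK, PD and dose-proportionality analyses do not use average daily dose. Nor does the SAP contain a miscalculated figure: the fault is in the rule, and it would appear only in the output.

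**What to change.** 1. In footnote [1] of Table 14.1.11, divide total dose by treatment duration in calendar days: last dose date minus first dose date plus 1. Listing 16.2.5.1 already defines duration this way.
2. State the same formula in the text of section 7.9, where average daily dose is currently named only in the heading.
3. Make footnote [2] explicit that days on treatment is this calendar span and not a count of days on which a dose was taken.
4. If Listing 16.2.5.3 is meant to report the same quantity, apply the same definition there; if it is a per-visit quantity, say so.

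The cost is two footnotes, one sentence in section 7.9 and one line of derivation code. No new data are needed and no other analysis changes. It should be settled before database lock.
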